#### 5.12.5 Need for Additional Glucocorticoid Doses

Use of hydrocortisone from the stress dosing packs or use of any additional glucocorticoid treatment during the study will be summarized descriptively.

#### 5.12.6 Laboratory Data

Descriptive statistics of the observed values and change from baseline (continuous data) will be presented by treatment group and visit for each hematology, urinalysis, and serum chemistry parameter. Each measurement (continuous data) will be classed as below, within, or above normal range, based on ranges supplied by the laboratory used. Shift tables in relation to the normal range from baseline to end of study/early withdrawal visit, and worst high/low on-treatment during the study will be presented. For the worst high/low shifts, all lab assessments will be considered (both scheduled and any unscheduled).

A listing of any clinically significant laboratory measurements recorded throughout the study will be presented.

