7.1. Discontinuation of Study Treatment

Events that will result in discontinuation of study treatment include:

- Inability to tolerate either study treatment secondary to perceived or observed side effects.
- Pregnancy (not due to safety reasons but because pregnancy may interfere with the primary endpoint)
- Any other changes to clinical signs or changes in laboratory values, physical status or AEs that could compromise the participant's status if they were to continue with the study treatment or if the Investigator feels that it is not in the best interests of the participant.

If a participant shows persistent signs of under-replacement on the starting dose of 30 mg Chronocort or IRHC they will be monitored and if symptoms do not resolve the participant should be withdrawn from study treatment. If a participant shows persistent signs of under-replacement during the titration period and has received at least 1 down titration of 5 mg, a reversion to the previous dose is permitted (i.e. an increase of 5 mg) after discussion with the medical monitor. If symptoms persist, no further dose increases can be made, and the participant should be withdrawn from study treatment (such cases should be discussed with the medical monitor).

If a participant discontinues study treatment, they should be placed onto the previous glucocorticoid treatment and dose they were receiving prior to entry into this study. They should complete as many of the assessments scheduled for Visit 6 as possible, preferably within 48 hours of stopping study treatment. In all cases except pregnancy (see Section 8.4.5 for handling of any pregnancies) the participant should be kept in the study, if the participant consents to this, and all further safety assessments conducted in line with the protocol schedule (note: no efficacy endpoints will be collected once the assessments detailed for Visit 6 [early withdrawal] are completed). The date the participant discontinues study treatment and the reason for discontinuation will be recorded on the participant's eCRF. Participants who have been randomized to study treatment and who discontinue from study treatment are not to be replaced. The handling of safety data collected after the participant has discontinued study treatment will be detailed in the SAP.

Participants who discontinue study treatment are not eligible to enter the long-term extension study (DIUR-015), except in the case of pregnancy (see Section 8.4.5).

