8.1.9. Telephone Call T5.2 (Week 22 ± 2 Weeks)

A telephone call will be made to all participants approximately 4 weeks after the last telephone call. All participants will be asked about any AEs or any other problems plus any changes in concomitant medications since their last visit. Any AEs or changes in concomitant medications will be recorded in the eCRF.

8.1.10. Visit 6 (End of Study/Early Withdrawal Visit - 28 Weeks + 1 Week From Randomization or at Point of Discontinuing Treatment or Withdrawing From the Study)

This visit is required for all participants either 28 weeks after randomization or at the time a participant withdraws early from treatment or from the whole study. The last dose of study medication will be taken in the morning of the last dosing day after the 08:00 hour androgen sample and optional saliva sample (where applicable) are collected. It is mandatory that this visit is conducted at the study site. If a participant who was enrolled under an earlier version of the protocol (where the study was up to 52 weeks in duration) had attended Visit 5 at Week 16 and is ongoing treatment, they must continue taking the study medication and must return at 28 weeks for the EOS (Visit 6) assessments. If they have already had more than 28 weeks of treatment then they must return as soon as possible (but not within 4 weeks of previous blood sampling) for the EOS (Visit 6) assessments according to this amendment. In the case of early withdrawal from treatment or from the study, as many assessments as possible should be completed within 48 hours of the last dose of the study medication. If the participant only discontinues study treatment, they should remain in the study where possible and be followed for safety assessments until the scheduled EOS visit (note: no efficacy endpoints will be collected once the assessments detailed for Visit 6 [early withdrawal] are completed).

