# 5.2.5 Participants Recruited before Implementation of Protocol Version 6.0

The week 28 visit was not scheduled prior to protocol version 6.0. Therefore some participants recruited before the implementation of protocol version 6.0 may be missing the week 28 assessment. In such cases, should the week 34 assessment be available, this will be used for the week 28 assessment. Therefore, where a week 34 assessment is available, no imputation for the missing week 28 assessment will occur. Furthermore, for participants recruited before the implementation of protocol version 6.0, if such a participant does not have a week 28 assessment, but their end of study is between week 16 and week 34, then the end of study is mapped to week 28.

Note, the following conventions will apply for the efficacy and safety analyses.

For efficacy data, all summaries will be presented by all available scheduled visits. In these summaries, week 28 and week 34 will be presented separately. In addition, a further summary, and where applicable analysis, will be performed for week 28 where week 34 assessments are mapped to week 28 as described above. Note, this will be the main analysis for inference.

For safety data, all summaries will be presented by all available scheduled visits. No mapping of week 34 to week 28 will occur.

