#### 5.2.13 Visit Windows

There are no plans to derive visit windows, and visits will be used in the analyses as reported on the eCRF. For participants prematurely withdrawing from the study, the early withdrawal visit will be remapped to the next scheduled visit after the last dose. Note, for participants with an end of study visit between weeks 28 and 34, the end of study visit will be remapped to week 28 for the analysis combining the week 28 and 34 results, see Section 5.2.5. Note, for participants recruited before implementation of protocol version 6.0 (see Section 5.2.5), week 34 assessments used in lieu of week 28 assessments will be used for analysis for the EES, as will any assessments from an end of study visit between week 28 and week 34.

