#### 5.2.14 Unscheduled Visits

Only scheduled post-baseline values will be tabulated. Post-baseline repeat / unscheduled assessments will in general be disregarded, although unscheduled visits will be included in the derivation of shifts to "worst" post-baseline value. All post-baseline assessments (scheduled and unscheduled) will be listed in the relevant appendices to the CSR.

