#### 5.4 Participant Disposition

Participant disposition will be summarized descriptively as follows:

- The number and percentage of participants achieving the following criteria will be summarized by treatment group and overall for the Screened Set:
  - Entering the study or failed screening, with reasons
  - Multiple screened and a) entering the study or b) persistent failed screening
  - Received IRHC in the run-in period but were not randomized, with reasons
  - Randomized
  - Included and excluded from each analysis set, with reasons for exclusion
  - Completed or prematurely discontinued treatment, with reasons (including the number of participants with premature discontinuation of study treatment, that continued study assessments)
  - Completed or prematurely discontinued study, with reasons
- As a separate summary, the number of participants included in each analysis set will be summarized for each region, country and study site by treatment group and overall for the Screened Set.
- The number of participants who complete each phase of the study and the number of participants present at each scheduled visit will be summarized by treatment group and overall for the FAS.

Participant disposition will be listed for the Screened Set. The reasons for exclusion from each of the analysis sets will also be listed.

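### The SAP sets no last-dose limit for the by-visit laboratory and vital-sign tables, so scheduled values taken after study drug stops count under Chronocort or IRHC

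*SAP*

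**What the plan says.** Protocol 7.1 covers participants who stop study treatment but do not leave the study. On treatment, "they should be placed onto the previous glucocorticoid treatment and dose they were receiving prior to entry into this study". On follow-up, the same section keeps consenting participants (pregnancy excepted) on the scheduled safety assessments, and Protocol 8.1.10 repeats that "they should remain in the study where possible and be followed for safety assessments until the scheduled EOS visit". On analysis, Protocol 7.1 defers: "The handling of safety data collected after the participant has discontinued study treatment will be detailed in the SAP".

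The SAP rules that reach the by-visit laboratory and vital-sign tables are these:

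- SAP 5.2.5: "For safety data, all summaries will be presented by all available scheduled visits".
- SAP 5.2.13: "There are no plans to derive visit windows, and visits will be used in the analyses as reported on the eCRF". Its next sentence moves the early-withdrawal visit of participants leaving the study to the next scheduled visit after the last dose.
- SAP 5.2.14: "Only scheduled post-baseline values will be tabulated".
- SAP 5.12.6, laboratory data: "Descriptive statistics of the observed values and change from baseline (continuous data) will be presented by treatment group and visit". SAP 5.12.7 has an equivalent sentence for vital signs.

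Elsewhere the SAP does use dosing. In 5.12.2, treatment-emergent adverse events end 30 days after the last dose, and later events get their own table. Section 5.12.3.2 defines subsequent medications. Sections 5.12.1 and 5.12.6 label the minimum/maximum and worst high/low shifts as on-treatment, without defining the term. Section 5.4 counts the "number of participants with premature discontinuation of study treatment, that continued study assessments".

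**The concern.** The protocol creates off-drug safety data by design and promises that the SAP will say what to do with them. For the by-visit laboratory and vital-sign tables, every applicable SAP rule is inclusive. A value taken on the pre-study steroid, which Protocol 5.1 allows to be hydrocortisone, prednisone, prednisolone or dexamethasone, would be averaged into the Chronocort or IRHC row for that visit. Nothing in the table would mark it.

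Comparing the arms on laboratory tests and vital signs is a stated safety objective (SAP Section 2). Intolerance and persistent under-replacement are among the reasons for stopping in Protocol 7.1, so the participants concerned are informative about safety. SAP Section 8, which lists departures from the protocol's analyses, does not mention this commitment.

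**Working it through.** The plan states no figure on this point, so there is none to reproduce. The check has two parts: what the rules do to one participant, and what share of an arm that could be.

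**Following one participant through the rules.** Suppose someone stops drug between Weeks 4 and 10, completes the early-withdrawal assessments (preferably within 48 hours), resumes the earlier steroid and attends Weeks 10 and 16 for safety. Both visits are scheduled, so 5.2.14 tabulates their values. 5.2.13 uses the visits as reported and 5.2.5 includes all available ones. 5.12.6 and 5.12.7 place them by group and visit. No step asks whether the value came after the last dose. The remapping sentence in 5.2.13 moves one visit and excludes none.

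**Visits affected.** Inputs: nominal visit days 28, 70, 112 and 196 (Weeks 4, 10, 16 and 28) and last-dose day s. A visit is off-drug if its day exceeds s, and beyond the adverse-event window if its day minus s exceeds 30. For example, with s from 29 to 69, the Week 10 gap is 70 − s = 1 to 41 days, the Week 16 gap is 112 − s = 43 to 83 days, and the Week 28 gap is 196 − s = 127 to 167 days.

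| Last-dose day | Later visits among Weeks 4, 10, 16 | More than 30 days after last dose | Later visits if a second Visit 6 is done at Week 28 | More than 30 days after last dose |
|---|---|---|---|---|
| 1–27 | 3 | 2 | 4 | 3 |
| 29–69 | 2 | 1 to 2 | 3 | 2 to 3 |
| 71–111 | 1 | 0 to 1 | 2 | 1 to 2 |
| 113–195 | 0 | 0 | 1 | 0 to 1 |

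An adverse event starting on a day counted in the third or fifth column would be tabled as non-treatment-emergent under 5.12.2, while a laboratory value from that day stays under the study drug.

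**Share of an arm.** The planned size is 25 per arm (SAP Section 3). The number k who stop and stay is an assumption. If all 25 contribute a value at a visit after those k have stopped, the off-drug share is k/25:

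- k = 1: 1/25 = 4%
- k = 2: 2/25 = 8%
- k = 3: 3/25 = 12%
- k = 5: 5/25 = 20%

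**Effect of a 30-day window.** Successive visits are 70 − 28 = 42, 112 − 70 = 42 and 196 − 112 = 84 days apart. All gaps exceed 30 days, so on the nominal schedule at most one scheduled visit per participant falls after stopping but inside the window.

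**The case against.** The strongest reply is that tabulating all scheduled safety values by group is a normal descriptive convention, and that the protocol's promise is largely kept. The SAP limits adverse events by last dose, tables later ones separately, defines subsequent medications, counts those who stopped drug but continued assessments, and labels the worst-value shifts on-treatment. Protocol 8.3.4 sends clinically relevant laboratory changes to the adverse-event page, where the last-dose rule applies. All of this stands. It narrows the gap to the by-visit tables and the undefined on-treatment label, but does not close it: the promised rule for these values is absent, and the default mixes them.

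The inclusive sentences also come from sections written for other purposes: Week 34 mapping, visit windows and unscheduled visits. That is fair. They are nevertheless the only rules available to a programmer.

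If the remapping rule were extended to people who stop drug but stay, the next visit row could hold a nearly on-drug value, reducing the counts above by up to one. Its wording covers only those leaving the study.

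Four stronger readings are tempting, and the documents do not support them:

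- *Week 28 is certainly affected, for example by a value 196 − 29 = 167 days after the last dose.* This needs a second Visit 6. Protocol 8.1.10 and the schedule of activities describe Visit 6 as at Week 28 or at stopping. Protocol 7.1's continued safety schedule points towards a second assessment but does not settle it.
- *The SAP contradicts its own statement that safety is presented by treatment received.* SAP 5.1 uses that phrase to assign participants to groups, not to classify individual visits.
- *The end-of-study laboratory and ECG shifts are contaminated.* The value used most naturally is the early-withdrawal one. The SAP does not say, so this is possible but not established.
- *Efficacy conclusions are at risk.* They do not draw on these tables.

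**Conclusion.** The point holds as a minor one. As written, the by-visit laboratory and vital-sign tables count scheduled values taken after study drug stops under Chronocort or IRHC, although Protocol 7.1 said the SAP would set out their handling. The size is unknown. Under the assumption that 1 to 5 of 25 in an arm stop and stay, it is 4% to 20% of that arm's values at a later intermediate visit, and the same at Week 28 only if a second Visit 6 assessment is done then. Staying requires consent, so the true number may be small. The documents give no basis for saying which parameter would shift, or by how much. Listings and the disposition and medication outputs would let a reader trace the values, but the tables themselves do not separate them.

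**What to change.** Add to the SAP:

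1. A flag on laboratory, vital-sign and ECG values built from the last-dose date (5.2.8 already covers missing dates). Define on-treatment as up to the last dose plus 30 days, to match the adverse-event rule, and always include the early-withdrawal visit.
2. Base the main by-visit tables and the on-treatment shifts on flagged values. Show later values in a separate post-discontinuation row or listing.
3. For participants who stop drug but stay, name the early-withdrawal visit as the end-of-study value in the laboratory and ECG shifts.

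The cost is a few sentences and one derived flag. It needs no new data, and no values are lost. The main tables would have slightly fewer late-visit values. A value within 30 days of the last dose may still have been taken on the earlier steroid, for at most one scheduled visit per participant on the nominal schedule. A shorter window would separate the steroids more cleanly, but could put an adverse event and its related laboratory value in different tables.

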#### 5.12.7 Vital Signs

Descriptive statistics for observed values and changes from baseline in the following vital signs will be presented by treatment group and visit:

- Systolic blood pressure (mmHg)
- Diastolic blood pressure (mmHg)
- Pulse rate (bpm)
- Respiration rate (breath / min)
- Body temperature (degrees Celsius)

# 5.12.8 Electrocardiogram Data

Descriptive statistics for observed values and changes from baseline in the following ECG variables will be tabulated at each follow-up:

- Heart rate (bpm)
- PR interval (ms)
- RR interval (ms)
- QRS complex (ms)
- QT interval (ms)
- QTc interval (ms)

In addition, shift tables relating to the overall interpretation (Normal, Abnormal NCS, and Abnormal CS) from baseline to end of study/early withdrawal visit will be presented by treatment group.

# 5.12.9 Physical Examination

The body systems within the physical examination data at the end of the study will be summarized by treatment group (Normal; Abnormal NCS, Abnormal CS). Changes from baseline will also be tabulated. Details of clinically significant findings will be listed.

# 6 INTERIM ANALYSIS

No formal interim analysis is planned.

# 7 DATA SAFETY MONITORING BOARD ANALYSIS

An independent DSMB will meet on a regular basis during the study to review safety data. The DSMB will operate in accordance with a charter, which is a separate controlled document.

Safety data will be generated at regular intervals for review by the independent DSMB (see Section 9.6 of the study protocol). Details of these DSMB outputs will be specified in the Kick-Off Meeting slides and minutes and the DSMB Charter. Any outputs provided to the DSMB will be unblinded (a separate statistical team will provide the unblinded outputs to the DSMB). Outputs provided to other team members to remain in a blinded capacity will use a dummy randomization list with generic labels.

During the course of the study, if unblinded analyses indicate that AEs are occurring more frequently than anticipated, the DSMB will notify the Sponsor, who will notify regulatory authorities expeditiously as appropriate.

# 8 CHANGES TO PLANNED PROTOCOL ANALYSIS

- Section 2: Analysis of Biochemical Response Rate at Week 4 was specified in the Protocol but not including a criterion for dose as the participant is still receiving the initial dose at Week 4. This analysis has been removed as it is identical to the analysis of Biochemical Control Rate at Week 4.
- No comparative analysis will be performed for the endpoint The change from baseline to 28 weeks of randomized treatment in size of TART (men only). Only summaries including percentage change from baseline will be provided.
- No compliance calculation will be performed. The extent by which participants did not follow the instructions for the return of unused and empty medication containers rendered calculations of compliance uninterpretable.

# 9 CHANGES TO PLANNED ANALYSIS FROM SAP VERSION 1.0

- In line with protocol amendment 6.0, the primary analysis timepoint has been updated from week 52 to week 28
- Sensitivity analyses of primary efficacy endpoint and first key secondary endpoint of MNAR multiple imputation and tipping point analysis have been removed.
- Analysis of second key secondary endpoint will now be mixed model repeated measures analysis. Analysis using MAR multiple imputation has been removed.
- Description of steps to be implemented in case of issues with statistical models, including potential exclusion of interaction term and/or other factors, was added.
- It was specified that all subgroup analyses will be performed as unstratified/unadjusted.
- Additional considerations for baseline derivation were added.

- The compliance calculation and analysis was removed.
- Updates to match to protocol version 7.0.

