# **3** SAMPLE SIZE

Sufficient participants will be screened to achieve approximately 50 participants randomly assigned to either Chronocort or IRHC (25 participants per treatment arm, regardless of baseline strata), or until a cut-off date of 30 April 2023, whichever is reached first. Individual study sites should not randomize more than 8 participants without first consulting the Sponsor. A sample size of 25 participants per treatment arm will provide at least 80% power to demonstrate non-inferiority of Chronocort to IRHC when the biochemical response rate in the IRHC arm is 40%, the non-inferiority margin is 15%, and the biochemical response rate in the Chronocort arm is 68% using a 1-sided continuity corrected z-test with unpooled variance and a 1-sided alpha of 2.5%. Sample size is calculated using PASS 2022 (v22.0.3).

Note: Basing the sample size calculation on a continuity corrected z-test provides a conservative estimate of sample size relative to the test, based on a logistic model adjusted for stratification factors, which will actually be used.

**Note:** Post-hoc analysis of study DIUR-005 showed that ~40% of participants receiving the control treatment (that is: their pre-randomization treatment) would have been down-titrated by the proposed rules for the current study at four weeks after randomization. Estimating therefore the response rate for the IRHC as 40% and expecting that no participants withdrawn completely from hydrocortisone treatment would qualify for down-titration, the estimated treatment benefit of IRHC is a gain in response rate of 40%. Setting the non-inferiority margin as minus 15% thus retains five eighths of the anticipated treatment benefit of IRHC.

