#### 5.11.2 Estimands

#### 5.11.2.1 Primary Efficacy Endpoint

Treatment Conditions of Interest	Chronocort vs IRHC		
Population	Participants Aged 16 Years and Over with Congenital Adrenal		
-	Hyperplasia		
Assessment	17-OHP and A4 plasma concentration obtained from the 08:00		
	hours bloo	d sample at Visit 6 (EOS) and daily dose of	
	hydrocorti	sone	
Outcome Variable	The proportion of participants in each treatment arm who are		
	biochemic	al responders at 08:00 hours at Visit 6 (EOS). See Section	
	5.11.1.1 for details on criteria for biochemical response		
Population-Level Summary	The differe	ence (Chronocort arm minus IRHC arm) in the proportion	
	of particip	ants who are biochemical responders at 08:00 hours at	
	Visit 6 (EC	DS)	
Analysis	The difference (Chronocort arm minus IRHC arm) in the proportion		
	of particip:	ants who are biochemical responders is estimated using	
	logistic reg	gression (Ge, 2011) with treatment, fludrocortisone use at	
	baseline, b	baseline, biochemical control at baseline, and the interaction of	
	fludrocortisone use and biochemical control at baseline as		
	explanatory variables.		
Intercurrent Events (ICEs)	(i)	Participants who withdraw from treatment before Visit	
		6 (EOS) or who do not meet the criteria for being a	
		biochemical responder are deemed not to be a	
		biochemical responder.	
	(ii)	Participants receiving rescue medication (under 'stress	
		dosing rules') will continue in the study with unchanged	
		procedures, except that Visit 6 (EOS) will be delayed if	
		necessary, to 5 days after the use of rescue medication	
Strategies to Handle ICEs	(i)	Discontinuation of study treatment before Visit 6	
		(EOS), for any reason	
		Composite strategy	
	(ii)	Receipt of rescue medication under 'stress-dosing rules'	
	()	Treatment policy strategy	

Where under the treatment policy strategy, available data occurring on or after the ICE will be analyzed as observed, and under the composite strategy, any observed biochemical response data

after the ICE will be considered as biochemical non-response. Additionally, any missing Visit 6 biochemical response data will be multiple imputed per Section 5.11.3.1.

**Interpretation:** Biochemical non-inferiority of Chronocort to IRHC will be declared if the 95% CI for the difference in proportions lies wholly above minus 15 percentage points. Confirmatory testing will occur on the primary estimand.

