# 5.11.3 Estimand Related Data Handling

#### 5.11.3.1 Primary Efficacy Endpoint – Biochemical Response at Visit 6 (EOS)

For the imputation of biochemical response where a composite variable strategy is employed, any biochemical response data occurring on or after the applicable ICE will be considered as biochemical non-response. This imputation will occur first, before any imputation of missing data occurs.

For the imputation of missing data, the binary response status will be multiple imputed. The number of imputations will be 50, representing the set of 50 plausible values obtained from a prediction model based primarily on observed data (i.e. applying a MAR approach in general). The fully conditional specification (FCS) method will be used for dealing with arbitrary non-monotone missing data patterns. The FCS is based on an iterative algorithm; at each iteration and for each variable of the prediction model, there is a prediction step and an imputation step. As imputations will be for binary components, the models used for prediction and imputation will be logistic regression models.

The full MI approach will comprise of 4 steps, as follows:

- Prediction Step: the current (iteration) values of the observed and imputed values are used to derive the predictive distribution of the missing values under MAR conditions
- Imputation Step: updated imputations are generated by draws from the predictive distribution defined by the updated logistic regression model
- Analysis Step: The analysis as described in Section 5.11.4.1 is conducted for each of the 50 imputations
- Combining Step: Rubin's rule (SAS PROC MIANALYZE) is used to combine the 50 point estimates and standard errors, in order to provide a single point estimate and confidence interval that can be compared to the respective Non-inferiority delta in the null hypotheses described in Section 5.11.1 to provide rejection or acceptance.

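### No remaining analysis tests a departure from MAR for the primary and first key secondary endpoints, and the imputation rule as written can pull early discontinuers into the MAR step

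*SAP*

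**What the plan says.** SAP Section 9 lists changes since version 1.0, among them: "Sensitivity analyses of primary efficacy endpoint and first key secondary endpoint of MNAR multiple imputation and tipping point analysis have been removed". It gives no reason.

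The confirmatory analysis of the primary endpoint has two steps. SAP 5.11.3.1 first applies the composite strategy: "any biochemical response data occurring on or after the applicable ICE will be considered as" non-response. Missing values are then filled by 50 multiple imputations under MAR. SAP 5.11.2.1 adds that "any missing Visit 6 biochemical response data will be multiple imputed per Section 5.11.3.1". SAP 5.11.3.2 takes a similar approach for dose response, the first key secondary endpoint.

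The same estimand table (5.11.2.1, intercurrent event (i)) states that participants who withdraw from treatment before Visit 6 are deemed non-responders. SAP Section 2 and Protocol Section 3 say this too, and include deaths.

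Two provisions determine which data a discontinuer has. Under Protocol 7.1, "no efficacy endpoints will be collected once the assessments detailed for Visit 6" (early withdrawal) are done. Under SAP 5.2.13, an early-withdrawal visit is remapped to the next scheduled visit after the last dose.

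The sensitivity analyses left in SAP 5.11.4.2 and 5.11.5.3 are subgroup and interaction analyses, with a supportive repeat on the Efficacy Evaluable Set (EES). Observed data are also summarized by visit without imputation.

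**The concern.** Non-inferiority is declared from a confidence limit that may include imputed responses. If missingness is related to outcome, MAR imputation can move that limit, and no planned analysis would show how far the assumption can fail before the conclusion changes. The trial is small: one participant is 4 percentage points of an arm of 25.

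The estimand statement and the computing rule also differ for one group, discontinuers with no Visit 6 record. The statement makes them non-responders; the rule, read literally, sends them to MAR imputation. Protocol 4.2 withdraws participants from treatment for persistent under-replacement, so some of these absences may reflect treatment failure. Because the testing is sequential, the outcome also governs whether the two key secondary claims can be made.

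**Working it through.** **Step 1. Reproduce the plan's own figure.** SAP Section 3 states: "A sample size of 25 participants per treatment arm will provide at least 80% power to demonstrate non-inferiority of Chronocort to IRHC". The inputs given there are assumed response rates of 40% on IRHC and 68% on Chronocort, a margin of 15 points, and a one-sided 2.5% z-test with continuity correction and unpooled variance.

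- Unpooled SE = sqrt(0.40×0.60/25 + 0.68×0.32/25) = sqrt(0.009600 + 0.008704) = 0.1353
- Power = Φ((0.28 + 0.15 − 1/25)/0.1353 − 1.96) = Φ(0.92) = 82.2%

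The stated power of at least 80% reproduces.

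**Step 2. Trace a discontinuer through the rules.**

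- *Stops after Week 16 and attends the early-withdrawal visit.* The next scheduled visit is Week 28, so a Visit 6 record exists and the composite rule recodes it to non-response. No gap.
- *Stops before Week 16.* The early-withdrawal visit is remapped to Week 4, 10 or 16. No efficacy data follow, so Visit 6 is empty. The composite step recodes the remapped record but has nothing to recode at Visit 6. That value is then missing and falls under the imputation rule. A recoded earlier non-response, where it enters the prediction model, may lower the imputed response probability but does not make it zero.
- *Stops at any time with no early-withdrawal assessment.* Visit 6 is again empty.
- *Recruited before protocol version 6.0.* SAP 5.2.5 maps a Week 34 assessment, or an end of study between Weeks 16 and 34, to Week 28. This narrows the gap for that group.

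**Step 3. Weight of one outcome for non-inferiority.** Unadjusted Wald 95% lower limit, 25 per arm: L = p1 − p2 − 1.96 × sqrt(p1(1−p1)/25 + p2(1−p2)/25).

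| Chronocort v IRHC responders | Difference | Lower limit (points) | Above −15? |
|---|---|---|---|
| 17 v 10 (planned rates) | +28 | +1.5 | yes |
| 16 v 10 | +24 | −2.9 | yes |
| 15 v 10 | +20 | −7.2 | yes |
| 14 v 10 | +16 | −11.3 | yes |
| 13 v 10 | +12 | −15.4 | no |
| 17 v 14 | +12 | −14.7 | yes |
| 17 v 15 | +8 | −18.5 | no |

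From the planned result, non-inferiority is lost after four adverse changes on Chronocort (17 to 13) or five on IRHC (10 to 15).

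Boundary example with a missing value: 13/24 observed plus one missing on Chronocort, against 10/25. Approximating MAR by a beta-binomial fill within arm, with Rubin's variance for 50 imputations, gives a lower limit of about −13.5 (non-inferior). Setting that one outcome to non-response gives −15.4 (not).

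**Step 4. How often this could matter.** With complete data, enumerating all outcome pairs, about 8% of trials at true rates 68%/40% are successes that a single adverse change would overturn. At 55%/40% it is about 12%.

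The next table gives the chance that non-inferiority is met under approximate MAR but lost in the worst case (missing Chronocort = non-response, missing IRHC = response). The numbers missing are assumed.

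| Missing | True 68%/40% | True 55%/40% |
|---|---|---|
| 1 in total | 5–6% | 9–10% |
| 1 per arm | 9% | 13% |
| 2 per arm | 19% | 23% |
| 3 per arm | 34% | 33% |

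**Step 5. First key secondary endpoint.** Its threshold is 0. No document gives dose-response rates. If they equalled 68%/40%, 17 v 10 gives +1.5 (superior) and 16 v 10 gives −2.9 (not), so one change at the expected result would decide it and close the gate to total daily dose (SAP 5.11.8).

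**The case against.** The strongest reply is that discontinuation is already handled conservatively. The SAP and the protocol both deem withdrawers non-responders for any reason, and the composite step comes before imputation. The protocol asks for early-withdrawal assessments, preferably within 48 hours, and Section 7.2 singles out androgens. A reader might infer that the plan intends to credit responses to participants who left because treatment failed. The documents do not support that: the stated estimand says the opposite, and the difficulty is a literal gap in the rule, mainly for those who stop before Week 16. That defence stands as to intent. It does not settle what would be programmed, since the computing rule refers only to existing data and then to any missing Visit 6 value.

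A reader might also infer that imputation goes wholly unchecked. It does not. The EES requires Visit 2 and Visit 6 androgens at 08:00, so it uses no imputed androgen result, and observed data are summarized without imputation. But the EES is a complete-case set that also drops critical deviators, and the summary is descriptive. Neither tests a departure from MAR.

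Finally, a reader might infer that one imputed outcome decides the trial. That holds only near the boundary. Sensitivity to single outcomes also belongs to any trial of 25 per arm and applies equally to observed results.

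The removal is disclosed and breaches nothing in the protocol, whose own sensitivity analyses address only variation in the treatment effect.

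**Conclusion.** The point holds in limited form. In the current text, no analysis tests a departure from MAR for the two endpoints that carry the first two confirmatory claims, and the imputation rule does not fully implement the composite strategy it states. Near the boundary a single imputed outcome can change the non-inferiority conclusion (−11.3 against −15.4 points); at the planned rates it takes four or five. With an assumed one to three missing outcomes per arm and true rates of 68%/40%, the chance of passing under MAR but failing in the worst case runs from 9% to 34%.

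These sizes rest on unadjusted Wald limits, 25 per arm and an approximate MAR fill. The covariate-adjusted limits that the SAP will use cannot be rebuilt without data, and the documents give no missing-data rate, so the actual exposure is unknown. This should be corrected, but it does not show that the planned conclusion is fragile.

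**What to change.** 1. In SAP 5.11.3.1, and by reference 5.11.3.2, state that any participant who discontinues treatment before Visit 6 is set to non-response whether or not a Visit 6 value exists. MAR imputation then applies only to other missing Visit 6 outcomes, and the rule matches the estimand in 5.11.2.
2. In SAP 5.11.4.2 and 5.11.5.3, prespecify a tipping-point analysis for the primary and first key secondary endpoints. Vary the number of responders among the remaining missing outcomes in each arm, include the worst case (missing Chronocort = non-response, missing IRHC = response), and mark where the lower limit crosses −15 points or 0. Treating missing as non-response in both arms is too weak a substitute: with 15/22 v 9/22 observed and three missing per arm, it gives 15 v 9 of 25 and a lower limit of −2.9, whereas the worst case gives 15 v 12 and −15.4.

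The cost is one sentence and one extra table. The downside for the sponsor is that a positive conclusion may be shown to be less robust.
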